6.4. Phase 3: Initial Testing of Treatment Efficacy

6.4.1. Overview. In this phase, appropriately classified patients will be assigned to participate in two memory interventions, one matched to their primary deficit, the other

mismatched, in counterbalanced order. The overall framework is outlined in Table 4; shaded cells are “matched” conditions.

6.4.2. Design. The overall approach is a ***multiple-subject Alternating Treatment Design***, effective for determining the relative efficacy of two treatments in a single individual⁸⁰. One participant will be assigned to each treatment order in Table 4, such that 4 patients per classification group (12 total) will participate. Each participant will receive 1 matched and 1

Table 4. Treatment Schedule

Memory Deficit	Treatment Strategy/Target			Treatment Orders (one matched, one mismatched; counterbalanced)
	Memory Strategy Training (1)	Errorless Learning (2)	Retrieval Practice (3)	
Encoding	+/+	+/-	+/-	12, 13, 21, 31
Consolidation	-/+	+//	+/-	21, 23, 12, 32
Retrieval	-/+	-/+	+//	31, 32, 13, 23

mismatched treatment, in counterbalanced order. Therapists will be blinded to patient classification.

Although this design is subject to multiple-treatment interference⁸¹ (the notion that the effects of each of the interventions might be affected by the presence of another intervention), such

[figure not shown]

Figure 1. Hypothetical data of two patients, one with encoding deficit (blue), the other with retrieval deficit (red).

carryover effects are typically small and counterbalancing the order of treatments should further reduce treatment carryover⁸⁰. The design permits comparison of treatment effects in conditions in which a treatment is given first vs. second. New methods for calculating treatment effect size and possible confounding factors are available⁸²⁻⁸⁵. ***It is hypothesized that greater gains in memory will be seen in matched, as compared to unmatched, treatments.*** This is illustrated by hypothetical data presented in Figure 1, where a patient with encoding deficits (blue) benefits more [greater elevation and slope] from memory strategy training than from retrieval practice, while the opposite pattern is seen

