in the patient with retrieval deficits (red). Each treatment will be conducted twice weekly for 3 weeks (6 sessions). Thus, each participant's involvement in actual treatment will span 6 weeks (2 treatments). Participants will be offered \$20/session for participation as inconvenience cost and to help them defray travel expenses. We will conduct a 1-month follow-up at which time performance on proximal outcomes (performance on VPA and FNP tasks) and secondary outcomes (see below) will be evaluated.

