## 2.6. Statistical Analysis Plan

The procedure for classifying participants into Encoding, Consolidation, and Retrieval groups is outlined in Section 2.3.2. It is recognized that, although patients will be classified according to their primary memory deficit, some may have relevant impairment in more than one domain. For this reason, each participant will be given a composite score for encoding, consolidation, and retrieval, and all three of these composite scores will be used in exploratory analyses of predictors of treatment response. Phase 2 neuropsychological scores (z-score transformed data using appropriate age- and education corrections) and neuroimaging data (NEW, FA, diffusivity measures, morphological volumes, TI from RS-fMRI for specific ROI pairs) will be analyzed using 1-way (Group: Encoding, Consolidation, Retrieval) ANOVAs followed by pairwise follow-ups with the Tukey HSD test. Dependent variables used to evaluate memory performance in Phase 3 are detailed in Section 2.2 above, and include session-wise percent correct data on VPA and FNP memory probes as well as post-treatment and 1-month follow-up probes. Data from Phase 3 will be analyzed by comparing effect sizes of matched and unmatched treatments at the individual subject level using methods described by Parker et al. These measures include (a) percentage of non-overlapping data points, (b) quantitative measures of improvement rate and difference level, and (c) Tau-U, a nonparametric measure of effect size that tests for differences in two treatments after trend adjustment. Additional measures will also be explored, including interrupted time-series/regression approaches and the last-day-of-treatment comparison approach. We will also evaluate the separate influence that severity of memory deficit has on treatment response (independent of patient grouping) by performing hierarchical linear regression in which severity is coded as average z-score on memory indices derived from phase 2, and patient grouping is dummy-coded.

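### Within-person Tau-U p-values in SAP 2.6 would be too small if neighbouring sessions are positively correlated, because each treatment is one unbroken run of six sessions and the plan makes no provision for serial dependence

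*SAP*

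**What the plan says.** Protocol 6.4.2 labels the design a "multiple-subject Alternating Treatment Design", but the schedule gives one block per treatment. "Each treatment will be conducted twice weekly for 3 weeks (6 sessions"), and "Thus, each participant's involvement in actual treatment will span 6 weeks (2 treatments"). The same section adds: "The design permits comparison of treatment effects in conditions in which a treatment is given first vs. second". Session-by-session alternation is not described. Table 4 assigns one participant to each order, so "4 patients per classification group (12 total) will participate".

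SAP 2.6 analyses Phase 3 by "comparing effect sizes of matched and unmatched treatments at the individual subject level", using session-wise percent-correct scores on verbal paired associates and face-name pairs. The measures are non-overlap, improvement rate and level difference, and "Tau-U, a nonparametric measure of effect size that tests for differences in two treatments after trend adjustment". It continues: "Additional measures will also be explored, including interrupted time-series/regression approaches and the last-day-of-treatment comparison approach".

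The SAP does not mention autocorrelation, an error structure for the time-series models, or a variance or reference distribution for Tau-U. It sets no significance level. Hypothesis A (Protocol section 5, Aim 2) nevertheless predicts a significantly larger benefit in the matched condition.

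**The concern.** Sessions are a few days apart. Fatigue, mood and effort can persist over days, so a participant's neighbouring scores may share error. When each treatment is one consecutive run, a slow drift falls mostly inside one block and looks like a difference between treatments. The usual Tau-U variance makes no allowance for that.

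A within-person comparison could then be declared significant through drift alone, with no treatment effect, learning trend or order effect. The Protocol means to use these results to power a larger trial, so such findings could carry forward.

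**Working it through.** **Inputs from the documents**
- Sessions per treatment: 2 per week × 3 weeks = 6 (Protocol 6.4), so 12 scores per person and material.
- Participants: 3 deficit groups × 4 orders = 12 (Protocol 6.4.2).
- Order balance (Table 4). Matched first: 12, 13 (encoding); 21, 23 (consolidation); 31, 32 (retrieval), which is 6 people. The other 6 orders are matched second.

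These counts reproduce the plan's figures of 6 sessions and 12 participants. The plan gives no significance level or power for Phase 3.

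**Assumptions:** two-sided 5% level; stationary first-order autoregressive errors with lag-1 correlation ρ; standard Tau-U variance under independence.

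**Standard variance.** Let S be the number of second-block scores above first-block scores, minus the number below, over all 36 pairs. Under independence Var(S) = 6 × 6 × 13 / 3 = 156, so SD = 12.49. The first-block trend score has variance 6 × 5 × 17 / 18 = 28.3. Trend-adjusted Tau-U therefore has variance 156 + 28.3 = 184.3.

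**Hand check at ρ = 0.3, using the difference in block means (unit-variance scores)**
- Variance of a block mean: [6 + 2(5ρ + 4ρ² + 3ρ³ + 2ρ⁴ + ρ⁵)] / 36 = 9.919 / 36 = 0.2755.
- Covariance between block means: (ρ + 2ρ² + 3ρ³ + 4ρ⁴ + 5ρ⁵ + 6ρ⁶ + 5ρ⁷ + …) / 36 = 0.611 / 36 = 0.0170.
- Variance of the difference: 2(0.2755 − 0.0170) = 0.517, against 2/6 = 0.333 under independence. The ratio is 1.55, so the true SD is about 1.25 times the assumed one.
- For S, simulation gives SD 15.4 against 12.49, a ratio of 1.23. The 1.96 cut-off is then worth 1.96 / 1.23 = 1.59, a true two-sided error of about 11%.

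**Simulated false-positive rates, no effect and no trend, nominal 5%**

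| ρ | Tau, first v. second block | Tau-U, trend-adjusted | Least-squares time series, level change (4 parameters) |
|---|---|---|---|
| −0.2 | 2.0% | 3.0% | 2.9% |
| 0 | 4.2% | 5.3% | 5.0% |
| 0.2 | 8.0% | 8.9% | 7.7% |
| 0.3 | 10.6% | 11.3% | 9.3% |
| 0.5 | 18.6% | 17.4% | 13.1% |

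If Tau-U is instead referred to a null distribution simulated from independent data, its rates at ρ = 0.2, 0.3 and 0.5 are 6.5%, 8% and 13%. The last column applies only if independent errors are fitted.

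**Scale.** At ρ = 0.3, Tau would falsely flag 12 × 0.107 = 1.3 participants per measure, against 12 × 0.041 = 0.5 under independence.

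**Role of the block schedule.** Alternating the treatments session by session on such series gives 4.2%, 2.0%, 1.4% and 0.7% at ρ = 0, 0.2, 0.3 and 0.5. The inflation comes from the single switch.

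**Can it be diagnosed?** With true ρ = 0.3, the lag-1 estimate from one person's 6 + 6 residuals averages −0.02 (SD 0.23). Twelve scores do not reveal the dependence.

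**Person-level alternative.** Take each person's second-minus-first difference, and compare the 6 matched-second with the 6 matched-first participants by a two-sample t test. The simulated size is 4.7% to 5.4% at ρ = 0, 0.3 and 0.5, with or without a common practice slope of 0.2 SD per session (assumed).

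The order adjustment is needed. That slope moves block means by 6 × 0.2 = 1.2 SD, in opposite directions for the two orders once differences are signed as matched minus mismatched. At ρ = 0.3 with the slope, an unadjusted one-sample test falls to about 0.02% size. Its power for an assumed 0.8 SD effect drops from 94% to 33%. The order-adjusted test keeps about 5% size and 93% power.

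**The case against.** **No decision rule.** SAP 2.6 presents Phase 3 as a comparison of effect sizes in a pilot, with no significance level. A reader might infer that participants will be labelled responders on the strength of these tests. The documents contain no responder rule, so that does not follow. What stands against the objection is narrower: the SAP says Tau-U tests for differences, Hypothesis A uses the language of significance, and no valid source for such a claim is specified.

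**Time-series models.** A reader might also infer that these treat sessions as independent. The SAP gives no error structure and calls them exploratory. The accurate statement is that the error model is missing.

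**Unknown correlation.** The size rests on an assumed ρ. Protocol 6.2.1 provides 144 pairs of each type (6 sessions × 2 lists × 12), so items are new at each session within a treatment, which may lower ρ. This objection stands in full as to magnitude.

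**Multiplicity.** Over 24 tests (12 people × 2 materials, taken as independent), Tau rates of 8% and 18% give a chance of at least one false difference of 1 − 0.92²⁴ = 0.86 and 1 − 0.82²⁴ = 0.99. It is tempting to blame serial dependence for that, but 24 tests at a true 5% already give 1 − 0.95²⁴ = 0.71. The per-test rates carry the point.

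**A larger neighbour.** A practice slope of 0.2 SD per session with ρ = 0 gives 36% false positives for Tau and 21% for trend-adjusted Tau-U. That is a separate problem. It does not remove this one, which arises with no trend, and the order-adjusted contrast handles both.

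**Conclusion.** The point holds in conditional form. The block schedule and the SAP's silence on serial dependence are facts of the documents. If within-person Tau-U p-values or intervals are computed with the usual independence variance, and neighbouring sessions are positively correlated, they overstate the evidence. At ρ = 0.3 the error is roughly double the nominal 5%; at ρ = 0.5 it is over three times nominal with the standard variance. The size also depends on which Tau-U variant and reference distribution are used, and the SAP states neither. At ρ = 0 there is no material inflation, and at ρ = −0.2 the tests are conservative. This is worth correcting, but it does not invalidate the individual effect sizes as description.

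**What to change.** In SAP 2.6:

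1. State that individual Tau-U, non-overlap and time-series results are descriptive effect sizes, reported without p-values or confidence intervals that assume independent sessions.
2. State that any significance claim for Hypothesis A rests on one matched-minus-mismatched contrast per participant, adjusted for treatment order. For example, compare second-minus-first differences between the 6 matched-second and the 6 matched-first participants, and take half the difference in group means as the estimate.

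The adjustment removes a practice trend common to both orders. It does not remove carryover that differs between orders, so the assumption in Protocol 6.4.2 that carryover is small should be repeated alongside it.

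The cost is a few sentences, with no new data, sessions or participants. The downside is that no result for a single participant can be called significant.

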Aim 2. Aim 2 is to provide a preliminary test of the response to the three memory interventions. At baseline, TBI survivors will be evaluated for memory function in each of these three memory component processes using established neuropsychometric methods. Their experimental treatment allocation will be to the treatment targeting their most impaired memory component. In addition, each subject will serve as his/her own control, by engaging in a treatment targeted to another memory component ('mismatched' group).

Hypothesis A. The matched vs. mismatched group will show differential improvement in memory component function, with the former group benefitting to a significantly greater degree. (Primary measures: Memory component performance, encoding, consolidation, retrieval; secondary: cognitive function and quality of life).

Aim 3. Aim 3 is to establish links between the behavioral taxonomy of the three memory components and differences in brain structure and function documented with diffusion tensor imaging and functional connectivity analysis. This is a key first step in establishing brain-based metrics of neuroplastic change after memory therapy in our research program.

Objective 3.1. Identify specific and unique imaging signatures that distinguish patients with deficits in encoding, consolidation, and retrieval, respectively. Primary measures: structural measures of morphometry and white matter integrity (FA) and functional connectivity (cross correlation and total interdependence) in identified brain networks damaged in TBI.

Clinical Implications. This research has the potential to devise a method to match specific

subcomponents of memory impairment to specifically targeted memory interventions, thus maximizing recovery of memory and function. The results of this investigation will be used to refine the interventions, to evaluate cognitive and functional endpoints, and to power a larger clinical trial that will yield data enabling clinicians to match TBI patients to effective treatments based on their individual profile of memory dysfunction.

6. Research Plan:

6.1. Study Design. The proposed research will be conducted in three phases: Intervention Development, Patient Characterization and Classification, and Initial Testing of Treatment Efficacy.

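### SAP 2.6 names no primary index, task or across-participant test for Hypothesis A, so support could be drawn from any of 8 to 12 index-by-task results

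*SAP*

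**What the plan says.** Protocol section 5, Aim 2, states Hypothesis A as a directional significance claim for matched over mismatched treatment, "with the former group benefitting to a significantly greater degree". The primary measure there is memory component performance (encoding, consolidation, retrieval). That is a construct, not a task, score or index. Protocol section 6.4.2 groups VPA and FNP together as proximal outcomes and ranks neither first.

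SAP 2.6 is the only Phase 3 analysis text available for review. The data "include session-wise percent correct data on VPA and FNP memory probes as well as post-treatment and 1-month follow-up probes". The analysis consists of "comparing effect sizes of matched and unmatched treatments at the individual subject level". The named measures are:

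- "a) percentage of non-overlapping data points"
- "b) quantitative measures of improvement rate and difference level", which is at least two indices
- Tau-U, described as "a nonparametric measure of effect size that tests for differences in two treatments after trend adjustment"

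The section then adds an open-ended list: "Additional measures will also be explored, including interrupted time-series/regression approaches and the last-day-of-treatment comparison approach". It gives no significance level, sidedness, multiplicity rule or rule for combining the 12 participants.

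**The concern.** A hypothesis worded in terms of significance needs one pre-stated quantity to decide it. Here the same data yield at least eight index-by-task results from the named measures and at least twelve with the exploratory ones. The time points and the several MST recall scores add more. Nothing says which result counts, or how many favourable ones are needed.

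Two things are at stake. First, a statement that matching works could rest on whichever index looked best. Second, the protocol intends to use these results to power a larger trial (section 5, clinical implications), and an effect carried forward because it was the best of several will be too large.

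A second, smaller issue concerns Tau-U. Used as a test within one person, it treats that person's consecutive sessions as independent observations.

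**Working it through.** **The plan's own figure.** Protocol section 6.4.2 and Table 4: 3 deficit groups × 4 treatment orders = 12 participants, which matches the stated total. This is a counterbalancing count. The documents give no power, alpha or familywise error rate to reproduce.

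**Count of results.** Four named indices × 2 tasks = 8. With the two exploratory indices, 6 × 2 = 12. Time points are not counted.

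**Chance of at least one false positive.** Independent tests at 5% would give 1 − 0.95^8 = 33.7% for eight. This is only an upper reference, because the indices share the same data. Correlation was therefore simulated with no treatment difference: 12 participants, 6 sessions per treatment, 2 tasks, and six indices per task, each tested by a paired t-test across participants (4,000 replicates per row). Assumptions that are not in the documents:

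- two-sided 5% and the across-participant t-test;
- a VPA-FNP correlation from 0 to 0.95;
- subject-by-treatment variation with SD 0.3 or 1.0 times the session-error SD.

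| Task correlation | Subject-by-treatment SD | 4 indices × 2 tasks | 6 × 2 | 6 × 2, favouring matched |
|---|---|---|---|---|
| 0 | 0.3 | 28.0% | 35.2% | 20.8% |
| 0 | 1.0 | 24.8% | 31.0% | 17.0% |
| 0.5 | 0.3 | 25.9% | 33.4% | 19.4% |
| 0.5 | 1.0 | 23.7% | 29.7% | 15.6% |
| 0.95 | 0.3 | 20.1% | 25.0% | 14.0% |
| 0.95 | 1.0 | 17.0% | 21.1% | 11.5% |

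Repeat runs under similar assumptions put the top of the six-index range at 36%. The ranges are thus 17-28% (17/5 = 3.4 to 28/5 = 5.6 times 5%) and 21-36% (21/5 = 4.2 to 36/5 = 7.2 times).

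For the four named indices, the rate favouring matched is about 10-15% against a nominal 2.5%. By symmetry it cannot be less than half the two-sided rate, which at the bottom row is 17.0/2 = 8.5%.

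**Tau-U within a person.** For 6 against 6 sessions, the statistic is the between-treatment comparison minus the first-block trend. Its variance under independence is 6·6·13/3 + 6·5·17/18 = 156 + 28.3 = 184.3. Simulated error at a nominal 5%, with lag-1 autocorrelation assumed:

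| Autocorrelation | No continuity correction | With correction |
|---|---|---|
| 0.2 | about 9% | about 6% |
| 0.3 | about 12% | about 8% |
| 0.5 | about 17% | about 13% |

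**Does a single across-participant mean make sense when the treatments are scored differently?** MST gives spontaneous and cued recall on the final trial (6.2.2.1), EL gives fifth-trial recall with guessing discouraged (6.2.3.1), and RP gives delayed recall (6.2.4.1). Tally Table 4:

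- Each treatment is matched in 4 orders.
- Each is mismatched in 4 orders (2 in each of the other two groups).
- Matched comes first in 2 orders per group, so in 6 of 12.

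Let s1, s2, s3 be additive scoring levels and p an additive second-period effect. The mean matched-minus-unmatched difference then contains [4(s1+s2+s3) − 4(s1+s2+s3)]/12 + (6p − 6p)/12 = 0. For one person, say with matched treatment 1 given first and treatment 2 second, the difference contains s1 − s2 − p, which does not cancel. The balanced group mean is therefore cleaner than the individual comparisons that the SAP plans.

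**The case against.** The strongest reply is that the SAP compares effect sizes within individuals and prescribes no group test, alpha or p-value. Non-overlap is descriptive unless a test is attached. The two further measures are labelled as explored. Level and rate are not interchangeable attempts, because protocol 6.4.2 predicts that both will be greater under matching. The study calls itself a pilot (6.3.2), and Aim 2 is a preliminary test.

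Much of this stands. The error rates above belong to an assumed procedure and must be quoted as a range with the assumptions. The exploratory label is fair, but the four named indices alone still give 17-28%. Pilot status limits the consequence without removing it, since the hypothesis is worded in terms of significance and the SAP describes Tau-U as a test.

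Two stronger readings are tempting, and the documents support neither.

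- A reader might infer that the plan, followed as written, declares success if any index on either task favours matching. No such rule is written. The SAP is silent, and silence is an omission.
- A reader might count individual Tau-U tests: 12 people × 2 tasks gives 1 − 0.975^24 = 46% for at least one significant matched benefit. That requires VPA and FNP to be independent within a person. With full correlation it is 1 − 0.975^12 = 26%. In either case, one significant person out of 12 is not Hypothesis A, so the figure should not be used.

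On autocorrelation, the documents give no value. New pairs at each session (144/6 = 24 per task, section 6.2.1) limit item carry-over, although six twice-weekly sessions in one person make some dependence plausible.

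**Conclusion.** The concern holds as a gap in specification. Hypothesis A is worded as a significance claim, but no index, task or across-participant test carries it, and the SAP has neither an alpha nor a decision rule. The plan therefore has no defined false-positive rate. The 17-28% and 21-36% show what could happen if every index were tested over participants at two-sided 5% and any favourable result were accepted. Where the rate falls in each range depends on the VPA-FNP correlation and the subject-by-treatment variation, neither of which is given. The upper ends need uncorrelated tasks, which is unlikely for two associative-learning tasks done by the same person in the same session.

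The Tau-U point is secondary. Error is about 9-17% for an assumed autocorrelation of 0.2 to 0.5, or about 6-13% with a continuity correction. This should be corrected before analysis. It does not undermine the design.

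**What to change.** Before analysis, amend SAP 2.6 to name one index and one score for Hypothesis A. For example, use each participant's matched-minus-unmatched mean level over the six sessions, averaged over VPA target recall and FNP name recall, and state whether the MST score is spontaneous or cued recall. Test it once across the 12 participants at two-sided 5%. Another index would serve equally well if it is fixed in advance.

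Report improvement rate (slope), the other indices, the separate tasks and individual Tau-U as descriptive effect sizes without significance tests. If all twelve tests are kept instead, Bonferroni needs 0.05/12 = 0.0042 per test, which is severe with 12 people.

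The cost is a short edit with no change to data collection. A favourable result on a non-primary index, including the slope that the protocol also predicts, can no longer be called significant. The cancellation of scoring and order effects needs all 12 orders in Table 4 to be completed. Those effects still widen the spread of the 12 differences, which costs some power.
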